### 3. Recipient of investigational, non-FDA approved medication

#### 6.0 Number of Subjects

70 patients will be randomized 1:1 (35 in each arm) in blocks of 10. Once a patient is randomized and receives at least one dose of CMV prophylaxis medication they will be included in the study in an intent-to-treat manner. Those that are lost to follow-up, withdraw, or are taken off study drug will not be replaced.

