For Aim 4, survey results will be aggregated using validated methods for each survey. The mean scores will be compared between treatment arms, as well as the mean change across the three measurement timepoints. Comparisons will be made using standard statistical tests based on the distribution of the results (Student's t-test for normal variance or the Mann-Whitney test for non-normally distributed data). Mean change will be assessed using general linear modeling (GLM) for repeated measures data with the appropriate link based on the distribution of the measures.

For Aim 5, interaction terms will be added to multivariable models (Cox regression or GLM) to assess if there are differences by race (race\*treatment) or sex (sex\*treatment). A p-value of <0.1 will be considered sufficient evidence of likely effect modification and the analysis will then be stratified by the appropriate variable (either race or sex) for a given outcome if there is in fact a significant interaction. Given the limited sample size, there is likely low power to detect statistically significant differences for this Aim; thus Aim 5 is considered exploratory in nature.

We will also assess for any impact of maribavir on tacrolimus dosing or trough concentrations. Steady-state stable doses of tacrolimus (mg/day) and whole blood trough concentrations will be assessed and compared in patients during maribavir therapy versus after completion of therapy. Changes will be compared between the treatment arms using difference in difference methodology to assess for drug-drug interactions. The level-normalized dose (dose needed to achieve a level of 8 ng/mL using linear proportions) will also be compared using difference-in-difference analysis. Finally, the proportion of patients in the maribavir arm that have more than a 10% change in level-normalized dose after discontinuing maribavir therapy will be collected and reported. These analyses are considered exploratory.

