The incidence of clinically significant leukopenia (WBC <3K AND dose reduction in MMF) is difficult to assess in the maribavir arm, as this specific issue is not reported in the published data. However, there are several studies that can be used to estimate this incidence for power/sample size purposes. In a study conducted in liver transplant patients, known to be at higher risk for cytopenias than kidney recipients, the incidence of neutropenia was 6% in the maribavir arm (Winston DJ et al Am J Transplant 2012;12:3021-30.). In a phase III prophylaxis study in allogeneic stem-cell transplants, who are very high risk for cytopenias, the incidence of neutropenia was similar between the maribavir, and placebo arms and the average WBC count was 4.2K in the placebo arm and 4.4K in the maribavir arm (Papanicolaou GA et al. Clin Inf Diseases 2019;68:1255-64.). Thus, maribavir does not appear to induce or worsen leukopenia and a 5% incidence is a reasonable expectation in the maribavir treatment arm for estimating sample size and power.

To meet at least 80% power, given an incident rate of 33 to 35% in the valganciclovir arm and 5 to 6% in the maribavir arm, 32 patients in each arm is required, assuming two independent samples, a two sided  $\alpha=0.05$ , and using the chi square test. This sample-size will be inflated to 35 patients per arm to address an expected dropout/lost to follow-up rate of 3-5% in each arm. Thus, 70 total patients, 35 in each arm, will provide adequate power to assess the primary aim of this study. SAS 9.4 (SAS Institute, Cary, NC) was utilized to conduct sample-size estimations (Proc Power).

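### The patient-level tacrolimus figure is planned in the maribavir arm only and without direction, so read alone it cannot be separated from trough variation or post-transplant drift

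*Combined protocol and SAP*

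**What the plan says.** Three tacrolimus analyses appear in one paragraph at the end of Statistical Methods (section 10.0).

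1. Dose and trough, on treatment against off it: "Steady-state stable doses of tacrolimus (mg/day) and whole blood trough concentrations will be assessed and compared in patients during maribavir therapy versus after completion of" (sentence cut one word short here). How the arms are contrasted follows: "Changes will be compared between the treatment arms using difference in difference methodology to assess for drug-drug interactions".
2. Level-normalized dose: "The level-normalized dose (dose needed to achieve a level of 8 ng/mL using linear proportions) will also be compared using difference-in-difference analysis".
3. Last, a patient-level summary to be reported: "the proportion of patients in the maribavir arm that have more than a 10% change in level-normalized dose after discontinuing maribavir therapy".

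The paragraph closes: "These analyses are considered exploratory".

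The first two analyses use the valganciclovir arm as control. The third does not. For the third, the plan gives no direction of change and no reason for the 10% cut-off. Nowhere does the plan give the number of troughs that define each period, the time windows, or an expected within-patient variability.

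**The concern.** A before-and-after change within one arm mixes three things: any effect of stopping maribavir, ordinary variation from trough to trough, and drift in dose and level as time since transplant increases. By using difference-in-difference for the mean change, the plan already accepts that a single-arm change is not enough. The patient-level count drops that control.

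The count also pools increases and decreases. If maribavir shifts tacrolimus exposure, the change on stopping should lean one way, whereas trough noise goes both ways. Pooling removes the feature that best tells the two apart.

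What is at stake is interpretation. This is the only planned statement of how many patients have a shift in tacrolimus requirement when maribavir stops, and a reader could easily take the whole proportion as maribavir's effect.

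**Working it through.** **No figure to reproduce.** The documents state no expected proportion, variability or power for the tacrolimus analyses. The check therefore asks how many patients would cross 10% if there were no interaction.

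**Inputs from the documents**
- Cut-off: more than 10% change, either direction, maribavir arm only (Statistical Methods).
- Level-normalized dose = dose × 8 / trough, from linear scaling to 8 ng/mL (Statistical Methods).
- 35 patients per arm (section 6.0).

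**Assumptions, not in the documents**
- Log-normal troughs with within-patient CV of 5–30%.
- *k* troughs per period, averaged geometrically, *k* = 1, 3 or 5.
- Constant dose, no drift and no interaction.

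**Formula.** With constant dose, the ratio *R* of level-normalized dose (after / during) is the mean trough during divided by the mean trough after. So

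SD of ln *R* = √ln(1 + CV²) × √(2/*k*)

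P(cross) = P(ln *R* > ln 1.10) + P(ln *R* < ln 0.90), with ln 1.10 = 0.0953 and ln 0.90 = −0.1054.

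**Worked case, CV 20%, *k* = 3.** √ln(1.04) = 0.198; × √(2/3) gives SD 0.162. The upper tail beyond 0.0953/0.162 is 27.8%, the lower tail beyond 0.1054/0.162 is 25.7%, and the total is 53.5%. Then 35 × 0.535 = 18.7, about 19 patients.

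**Share crossing 10% with no interaction**

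| Assumed CV | 1 trough | 3 troughs | 5 troughs |
|---|---|---|---|
| 5% | 16% | 1.5% | 0.2% |
| 10% | 48% | 22% | 11% |
| 15% | 63% | 41% | 29% |
| 20% | 72% | 54% | 42% |
| 30% | 81% | 68% | 59% |

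Half of patients cross by chance once the CV reaches about 10.5% (1 trough), 18% (3) or 24% (5).

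**Unequal periods.** The assessment table in section 10.0 lists tacrolimus levels at days 3 and 7, weeks 2 and 4, and months 3, 6 and 12. D+/R− patients complete prophylaxis at 6 months, so month 12 is their only listed level clearly after therapy; the others have months 6 and 12. Replacing √(2/*k*) by √(1/3 + 1/*m*), for 3 troughs during and *m* after:
- *m* = 1: 8%, 38%, 56% and 66% at CV 5%, 10%, 15% and 20%.
- *m* = 2: 3%, 27%, 46% and 58%.

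The same section says all accessible record data will be gathered, including outside laboratories, so the real trough count may be higher.

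**What direction adds (CV 20%, *k* = 3).** Suppose level-normalized dose truly rises by 20% on stopping; add ln 1.2 = 0.182 to the mean of ln *R*. The pooled proportion goes from 54% to 74%. Split by direction, increases go from 28% to 71% and decreases fall from 26% to 4%. The split shows the shift much more clearly.

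**The case against.** The strongest reply is that the plan does not rest the interaction on this count. The paragraph names between-arm difference-in-difference as the method for drug-drug interactions and applies it to dose, trough and level-normalized dose. That comparison removes shared drift on average, and it keeps the sign. The proportion comes last, is only to be reported, and sits under an exploratory label. All of this stands. A reader might infer that the trial summarises the interaction by an uncontrolled count, or has no controlled assessment of it; the documents say otherwise.

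A second reply is that nothing in the documents shows 10% to be crossed often. This also stands. At CV 5% with 3 troughs only 1.5% cross, and the restriction to stable doses at steady state may lower variation, although that restriction is not defined. Nor is the figure always uninformative: at CV 10% with 5 troughs, a true 20% rise would move it from 11% to 92%. But at CV 20% with one trough the same rise moves it only from 72% to 77%. Without a control count, a reader cannot tell which situation applies.

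A third reply is that a control count adds little inference. At CV 20% with 3 troughs, comparing the pooled proportions between arms (35 per arm, two-sided 5%) has power of about 0.44 for a true 20% rise, whereas the planned difference-in-difference, taken on the log scale, has 80% power for a change of about 11%. This is correct, and it is why the count should remain a descriptive supplement.

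**Conclusion.** The point holds in a limited form and is minor. The interaction assessment itself is controlled. The accompanying patient-level proportion is not: it is planned in one arm and without direction, so on its own it cannot be separated from trough variation or from drift with time since transplant.

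The one-arm, undirected design is read directly from the text. The size of the background is not. It depends on an assumed CV and trough count and runs from about 0.2% to 81% over the ranges above, with 54% (about 19 of 35) at CV 20% and 3 troughs. Drift is left out of these figures because the documents give nothing to size it.

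Two stronger readings are not supported: that ordinary variation is known to cross 10% often, and that the trial cannot show an interaction. Tacrolimus exposure is in none of the five aims and none of the 18 listed endpoints, so no primary or secondary result and no sample-size figure is affected.

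**What to change.** Amend the last reporting sentence of the tacrolimus paragraph so that it:
- gives the proportion with more than a 10% change in level-normalized dose in both arms, after stopping maribavir and after stopping valganciclovir, over matched windows;
- counts increases and decreases separately;
- gives the between-arm difference with a 95% confidence interval;
- states how many troughs define each period;
- labels the result a descriptive supplement to the difference-in-difference.

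The cost is a sentence or two in the analysis plan. Tacrolimus levels and doses are already collected in both arms, and the difference-in-difference already needs them. No patient procedure or treatment changes.

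The one drawback is imprecision. With 35 per arm and both proportions near 0.535, the 95% interval for the difference is about ±1.96 × √(2 × 0.535 × 0.465 / 35) = ±0.23. The text should say that the comparison is not meant as a test.

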### **Power/Sample Size**

This study is adequately powered to detect a clinically meaningful and statistically significant difference in the incidence of clinically significant leukopenia in those randomized to maribavir vs. valganciclovir under most incident rate scenarios. For this study, clinically significant leukopenia is defined as a WBC count of <3,000 AND a reduction in the dose of mycophenolate or valganciclovir dose. Based on a retrospective analysis of internal data, the expected incidence of clinically significant leukopenia in the valganciclovir arm is between 33 and 35%. To support this incident rate, we conducted a retrospective analysis of our internal data to fully assess the incidence of clinically significant leukopenia. In this analysis, we included 446 adult kidney transplant recipients transplanted at MUSC between 2007 and 2015. We chose this time period as we had comprehensive data on induction, WBC counts, and MMF dosing to allow for assessment of the incidence of clinically significant leukopenia. Of these patients, 127 (28%) received rATG induction. The incidence of WBC <3K with and without MMF dose reduction is detailed in the table below, which was assessed within 1 year of transplant. This data matches our expected incidence of leukopenia in the VGC arm of 35%. This is because patients in the proposed study will be receiving rATG or be CMV D+/R- and receive 6-months of VCG/maribavir and be at higher risk of leukopenia.

[figure not shown]
Induction Agent	N	WBC <3K	WBC <3K and MMF Dose Reduction
Basiliximab	319	36.7%	21.3%
rATG	127	56.7%	34.6%

The incidence of clinically significant leukopenia (WBC <3K AND dose reduction in MMF) is difficult to assess in the maribavir arm, as this specific issue is not reported in the published data. However, there are several studies that can be used to estimate this incidence for power/sample size purposes. In a study conducted in liver transplant patients, known to be at higher risk for cytopenias than kidney recipients, the incidence of neutropenia was 6% in the maribavir arm (Winston DJ et al Am J Transplant 2012;12:3021-30.). In a phase III prophylaxis study in allogeneic stem-cell transplants, who are very high risk for cytopenias, the incidence of neutropenia was similar between the maribavir, and placebo arms and the average WBC count was 4.2K in the placebo arm and 4.4K in the maribavir arm (Papanicolaou GA et al. Clin Inf Diseases 2019;68:1255-64.). Thus, maribavir does not appear to induce or worsen leukopenia and a 5% incidence is a reasonable expectation in the maribavir treatment arm for estimating sample size and power.

To meet at least 80% power, given an incident rate of 33 to 35% in the valganciclovir arm and 5 to 6% in the maribavir arm, 32 patients in each arm is required, assuming two independent samples, a two sided  $\alpha=0.05$ , and using the chi square test. This sample-size will be inflated to 35 patients per arm to address an expected dropout/lost to follow-up rate of 3-5% in each arm. Thus, 70 total patients, 35 in each arm, will provide adequate power to assess the primary aim of this study. SAS 9.4 (SAS Institute, Cary, NC) was utilized to conduct sample-size estimations (Proc Power).

For comprehensiveness, we conducted 17 different power/sample size analyses to assess different incident rates of clinically significant leukopenia in both the valganciclovir arm and maribavir arm. These ranged from 30-35% in the valganciclovir arm and 5-10% in the maribavir arm. The results are summarized in the table below. With a sample size of 70 patients, 35 in each arm, we have adequate power to determine statistically significant differences between arms in 71% of these incident rate scenarios. The figure below this table displays the varying power estimates from 0.5 to 0.95 based on the 12 most likely incident rate scenarios for leukopenia with valganciclovir and maribavir and the estimated required sample sizes needed for these power calculations. Based on these incident rate estimates, adequate power is achieved for sample sizes between 50 and 75 patients in these scenarios. Required sample sizes beyond 70 patients are not common and appear to depend more on higher rates of leukopenia in the maribavir arm (increasing above 7%) vs. lower rates of leukopenia in the valganciclovir arm (decreasing below 32%).

Incidence of Leukopenia in the Valganciclovir Group	Incidence of Leukopenia in the Maribavir Group	N Total	Actual Power	N Total with 5% Inflation Due to Dropouts	N Total with 3% Inflation Due to Dropouts
0.35	0.05	52	0.81	55	54
0.35	0.06	58	0.813	61	60
0.35	0.07	62	0.801	66	64
0.35	0.08	70	0.809	74	73
0.35	0.09	76	0.802	80	79
0.35	0.10	84	0.802	89	87
0.34	0.05	54	0.805	57	56
0.33	0.05	58	0.812	61	60
0.32	0.05	60	0.805	63	62
0.31	0.05	61	0.808	65	63
0.30	0.05	68	0.809	72	71
0.34	0.06	60	0.806	63	62
0.33	0.07	70	0.803	74	73
0.32	0.08	84	0.807	89	87
0.31	0.09	100	0.803	105	103
0.30	0.10	122	0.803	129	126
0.33	0.06	64	0.809	68	66

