Maribavir has been evaluated for the prevention of CMV infection in phase II and phase III trials within allogeneic stem cell transplant recipients. At 6-months post-transplant, the rates of CMV infection using PCR were not different between treatment and placebo arms, although the rates of pp65 antigenemia were lower in the maribavir group. However, these studies used a low dose of 100mg PO BID. In subsequent studies within solid organ transplantation, maribavir dosed at 400 to 1200mg PO BID was equally efficacious to valganciclovir for the treatment of CMV infection. Of note and importance to this proposal, the rates of neutropenia were 4-5% in the maribavir treated patients vs. 15-18% in valganciclovir patients. Thus, at an appropriate dose, maribavir appears to have similar efficacy to valganciclovir in treating CMV infection with a significantly reduced incidence of neutropenia. Currently, there is a lack of randomized controlled trials assessing the safety and efficacy of adequately dosed ( $\geq 400$ mg PO BID) maribavir for the prevention of CMV infection in solid organ transplant recipients.

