### **Statistical Methods**

The analyses to assess for study Aims will be conducted using standard and widely accepted statistical methods. Data will be reported using percentages for nominal variables and univariate comparisons using Fisher's exact test or Pearson's chi-squared test as appropriate. This includes baseline demographics and transplant characteristics, as well as the non-time to event outcome

variables. For continuous variables with normal distribution, results will be reported using means and standard deviations with univariate statistical comparison using Student's t-test for two independent samples. For non-normally distributed variables, data will be reported using medians and interquartile ranges, with univariate statistical comparison conducted using the Mann Whitney U test. Normal distribution of continuous variables will be assessed using normality plots and the Shapiro-Wilk test. Normal variance will be assessed using Levene's test for equality of variances. Chi square or Fisher's exact test will be used for univariate assessments of key outcomes, including the incidence of leukopenia, neutropenia, CMV antiviral prophylaxis dosing interruption, CMV infection, acute rejection, graft loss and death.

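### The 71% of scenarios said to be adequately powered at 70 patients is a count before dropout; the plan's own dropout columns give 53%, and the result also depends on a test the plan leaves open

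*Combined protocol and SAP*

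**What the plan says.** Section 6.0 sets the enrolment: "70 patients will be randomized 1:1 (35 in each arm) in blocks of 10". It adds that patients who are lost, withdraw or stop study drug are not replaced.

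Power/Sample Size (in section 10.0) derives 32 per arm for 80% power at 33-35% on valganciclovir versus 5-6% on maribavir, with two-sided alpha 0.05 and a chi-square test whose type is not stated. It then says: "This sample-size will be inflated to 35 patients per arm to address an expected dropout/lost to follow-up rate of 3-5% in each arm".

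A table of 17 incidence pairs follows. It gives a total N, the power at that N, and two further totals inflated for 5% and 3% dropout. The text draws this conclusion: "With a sample size of 70 patients, 35 in each arm, we have adequate power to determine statistically significant differences between arms in 71" per cent of the scenarios. It also says: "Required sample sizes beyond 70 patients are not common".

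For the analysis, Statistical Methods says: "Chi square or Fisher's exact test will be used for univariate assessments of key outcomes, including the incidence of leukopenia". An earlier sentence there names Pearson's version as the chi-square.

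On the maribavir rate, the plan says that the composite endpoint is not reported in published data. It cites 6% neutropenia in liver recipients and, from a stem-cell study, neutropenia and mean white-cell counts similar to placebo. It concludes: "Thus, maribavir does not appear to induce or worsen leukopenia and a 5% incidence is a reasonable expectation in the maribavir treatment arm".

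**The concern.** The plan enrols the number that includes dropout but supports its power claim with the column that excludes it. A scenario needing 70 evaluable patients is counted as covered by 70 enrolled, although the plan expects to lose 3-5% of them.

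The choice of test is a second gap. With event rates near 5% in one arm and about 35 patients per arm, Pearson and Fisher differ materially in power. A table computed for a third test describes neither exactly.

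What is at stake is how the trial is read. A funder or ethics board would take 71% as the robustness of the primary aim, and a null result would be interpreted against that statement.

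**Working it through.** **Inputs.** Incidence pairs, N, power and inflated totals: table in Power/Sample Size. Enrolment of 70, no replacement: section 6.0. Dropout 3-5%, two-sided alpha 0.05, target power 80%: Power/Sample Size. Analysis tests: Statistical Methods.

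**1. Reproduce the 71%.** Rows with uninflated N of 70 or less: 12 of 17. 12/17 = 70.6%, which is the stated figure.

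**2. Count after dropout.** The inflated columns equal N × 1.05 and N × 1.03, rounded up. Three rows leave the count:

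| Valganciclovir / maribavir | N | with 5% | with 3% |
|---|---|---|---|
| 0.35 / 0.08 | 70 | 74 | 73 |
| 0.30 / 0.05 | 68 | 72 | 71 |
| 0.33 / 0.07 | 70 | 74 | 73 |

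That leaves 9/17 = 52.9% in either column, and 8/17 = 47.1% need more than 70. Dividing by (1 − dropout) instead gives the same count.

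**3. Headline case.** The six rows with 33-35% versus 5-6% have 5%-inflated totals of 55, 61, 57, 63, 61 and 68. All fit within 70.

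**4. Which test produced the table.** For the likelihood-ratio chi-square, with p̄ the mean of the two rates,

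δ = N × Σ [p ln(p/p̄) + (1−p) ln((1−p)/(1−p̄))], summed over the two arms; power = Φ(√δ − 1.96).

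For 0.33 versus 0.06, N = 64, p̄ = 0.195: the sum is 0.1736 − 0.1230 − 0.0707 + 0.1457 = 0.1256, so δ = 8.04, √δ = 2.836 and power = Φ(0.876) = 0.809, as printed. This formula agrees with the printed power to within 0.001 in 16 of 17 rows.

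The usual Pearson formula at 32 per arm gives Φ[(0.27√32 − 1.96√(2 × 0.195 × 0.805)) / √(0.2211 + 0.0564)] = Φ[(1.527 − 1.098)/0.527] = 0.792. Enumerating all binomial outcomes, Fisher's exact test gives 0.725 and uncorrected Pearson 0.826.

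**5. Count by test.** Exact power by enumeration over the 17 pairs; 33 per arm is 35 × 0.95 = 33.25, rounded down.

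| Test | at least 80% at 35 per arm | at least 80% at 33 per arm |
|---|---|---|
| Uncorrected Pearson | 12/17 (71%) | 11/17 (65%) |
| Fisher's exact | 6/17 (35%) | 2/17 (12%) |

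In the six headline rows, exact Pearson power at 33 per arm is 0.84-0.91. Fisher gives 0.78-0.87 at 35 per arm and 0.74-0.84 at 33.

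**6. The row that does not match.** For 0.31 versus 0.05 the table prints N = 61, which cannot be split 1:1, with power 0.808. The likelihood-ratio formula gives 0.789 at 61 and 0.808 at 64. The printed inflated totals, 65 and 63, follow from 61 (64.05 and 62.83, rounded up). From 64 they would be 68 (67.2) and 66 (65.92). No count changes.

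**The case against.** The best defence is that the sample size was set for the headline rates, was explicitly raised from 32 to 35 per arm for dropout, and passes at those rates after inflation. The table prints both dropout columns openly. This stands: the fault is in a summary sentence, not in the chosen N.

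A second defence is that exact uncorrected Pearson power is higher than the formula suggests. With 67 evaluable patients (34 + 33) it still reaches 80% in 12 of 17 scenarios, and the likelihood-ratio method at 67 gives 10 of 17. This also stands, and it limits what 53% means. It is the share of rows whose inflated requirement fits within 70, as the plan computes it; it is not a test-independent share with 80% power. It does not rescue the sentence, because the plan has not committed to that test and Fisher gives far lower counts. Nor is Fisher certain to be used: at 35% versus 5% the expected count in the event cells is 35 × 0.20 = 7.

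Third, the statement about sizes above 70 follows a reference to a figure of the 12 most likely scenarios, which is not in the available text. It may refer to that figure, so qualifying it is fairer than deleting it.

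Two stronger readings are tempting. A reader might infer that 53% makes the trial a near coin-flip; but it is a share of an unweighted list of scenarios, not a probability of success, and 9 of 17 is still literally most of them. A reader might also scale the internal 34.6% by the neutropenia ratio in section 2.0 ("the rates of neutropenia were 4-5% in the maribavir treated patients vs. 15-18% in valganciclovir patients") to get 7.7-11.5% on maribavir (34.6% × 4/18 to 34.6% × 5/15), and treat about 8-12% as the proper planning range. The documents do not support that step: it applies a ratio from CMV treatment studies to a different composite endpoint. The plan also discloses that the endpoint is unreported for maribavir, cites white-cell counts as well as neutropenia, and tabulates rates up to 10%.

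**Conclusion.** The concern holds as a should-fix reporting error. On the plan's own dropout columns, 9 of 17 scenarios (53%) fit within 70 enrolled, against the stated 71%. This needs no assumption beyond the plan's table, its 3-5% dropout and its rule of no replacement. By the table's method, 70 remains sufficient for the headline rates.

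The effect of the open choice of test is larger than that of dropout: 12 versus 6 scenarios at 35 per arm, and 11 versus 2 at 33. It assumes binomial outcomes, two-sided 0.05 and no continuity correction for Pearson. That the table rests on a likelihood-ratio test is inferred from the numerical match; the plan does not name it.

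The 5-6% maribavir rate is a proxy: no cited figure measures a low white-cell count with a dose reduction in maribavir-treated patients. The documents do not establish a better value.

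**What to change.** - **Scenario count.** Say that, after inflation for 3-5% dropout, 9 of 17 scenarios (53%) need no more than 70 patients, and that 12 of 17 (71%) is the figure before dropout. Qualify the statement about requirements above 70 to match: 8 of the 17 tabulated scenarios exceed it after inflation.
- **Test.** Name one primary test for the leukopenia endpoint in Statistical Methods. Recompute the table and the scenario count for that test at 35 and about 33 per arm, and report whatever count results.
- **Row 0.31 / 0.05.** Change N to 64 and the inflated totals to 68 and 66.
- **Maribavir rate.** State that 5-6% is a proxy drawn mainly from neutropenia data, without substituting another planning range.

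The cost is a short recalculation and edits to one section and one table. The stated figure becomes less favourable; enrolment does not change.
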